results support the efficacy of letrozole-associated controlled ovarian stimulation followed by embryo/oocyte cryopreservation in breast cancer patients, the numbers remain low to draw solid conclusions.

In young breast cancer patients, specifically in those with endocrine-sensitive disease, the need for controlled ovarian stimulation raises specific issues to be taken into account during oncofertility counseling related to its possible negative impact on their prognosis [12]. During standard controlled ovarian stimulation, estradiol levels rise up to 10-20 times higher than in natural cycles. Although the high estradiol levels during controlled ovarian stimulation cycles is temporarily limited to a couple of weeks, many oncologists and breast cancer patients are concerned about the use of these techniques fearing that the high estrogenic state can promote cancer growth or recurrence [9]. Therefore, controlled ovarian stimulation protocols with the addition of letrozole have been specifically designed for breast cancer patients to limit the potential negative impact of the short-term increase in estradiol levels while maintaining a good oocyte yield [18]. To date, only one single-center prospective study investigated the safety of controlled ovarian stimulation before chemotherapy initiation in breast cancer patients [24,25]. Patients interested in embryo cryopreservation underwent controlled ovarian stimulation with letrozole while women who did not receive any fertility-preserving procedure served as controls. The analysis after approximately 2 years of median follow-up included 79 patients who underwent controlled ovarian stimulation for embryo cryopreservation and 136 controls [24]. Patients in the controlled ovarian stimulation group had a trend for higher estrogen-receptor positivity ( $p = 0.08$ ). The study showed no difference in survival outcomes, with a hazard ratio (HR) for recurrence after embryo cryopreservation of 0.56 (95% confidence intervals [CI], 0.17-1.9;  $p = 0.36$ ) [24]. A recent update of the study included 337 women, of whom 120 underwent controlled ovarian stimulation with letrozole prior to chemotherapy and 217 did not undergo any fertility-preserving procedure [25]. Patients in the control group had significantly more frequent lymph-node

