### 3.2. Data collection

For all consecutive eligible patients included in the study, anonymized data will be entered into ad hoc electronic Case Report Forms (eCRF). The following information will be collected:

1) Baseline characteristics (at study inclusion): BMI; smoking habit; age at menarche; use of birth control pills; prior children before breast cancer diagnosis; history of spontaneous or induced abortion; prior treatment for infertility; prior gynecological surgery and/or medical history with possible impact on fertility; baseline AMH value.

- 2) Breast cancer history: date of diagnosis; age at diagnosis; disease stage; type of breast and axillary surgery; histology; tumor size and nodal status (for patients who underwent primary systemic therapy, both clinical tumor size and nodal status before treatment initiation and pathological tumor size and nodal status at the time of surgery will be collected); grade; hormone receptor status (estrogen and progesterone receptors); HER2 status.
- 3) Treatment of the primary tumor: timing of systemic therapy administration (adjuvant or neoadjuvant); use of chemotherapy (type and number of cycles); use of endocrine therapy (type and duration); use of anti-HER2 targeted therapy (type and duration); use of radiotherapy; use of breast reconstruction surgery.
- 4) Survival status: any recurrence of invasive breast cancer including date of the event; type of recurrence of invasive breast cancer (locoregional or distant event); any second primary contralateral breast cancer including date of the event; any second primary malignancy including date of the event; date of last follow-up and/or death.
- 5) Controlled ovarian stimulation protocol: type of stimulation (follicular or random); total FSH dose; number of stimulation days; number of days with antagonist; estradiol and progesterone levels at triggering and during luteal phase (L3-L8); number of oocyte/embryo collected; number of mature oocytes collected; maturation rate; number of oocyte/embryo cryopreserved; number of patients with poor response; number of patients with stimulation failure.
- 6) Ovarian function before and after chemotherapy: treatment-induced amenorrhea; age at menopause; AMH values.
- 7) Pregnancy after breast cancer: any pregnancy including date of the event; pregnancy outcome; gestational age at delivery; pregnancy/fetal/obstetrical outcomes; breastfeeding and its duration; use and type of assisted reproductive technology.

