#### **4.4. Laboratory procedures for circulating tumor DNA**

Three blood samples of 10 ml should be collected in EDTA tubes; two samples will be centrifuged within 1 hour from collection, to separate plasma from peripheral blood cells, at 820g for 10 minutes at  $4^{\circ}\text{C}$ . Recover and transfer plasma (the top yellowish layer of the tube content) into new micro tubes, compatible with high-speed centrifuge. Centrifuge the plasma at maximum speed (if available 20000g is recommended) for 10 minutes at  $4^{\circ}\text{C}$ . Transfer all plasma into cryovials and stored at  $-80^{\circ}$ . The 3rd sample of whole blood will be stored directly at  $-80^{\circ}\text{C}$ . Blood and plasma samples will be shipped on dry ice to the central laboratory (Erasmus hospital) at fixed time points for evaluation.

Plasma samples will be collected at enrollment (i.e. at the time of oncofertility counseling/breast cancer diagnosis) before starting chemotherapy (and before starting controlled ovarian stimulation in patients who access oocyte/embryo cryopreservation), Then, this analysis will be repeated at the end of controlled ovarian stimulation, and at relapse or end of follow-up.

In this study, evaluation of the circulating tumor DNA (ctDNA) in the plasma will be performed. The aim is to 1) evaluate the effect of controlled ovarian stimulation on the levels of ctDNA and correlate

with risk of recurrence and 2) to evaluate the pattern of somatic mutations in young breast cancer patients.

Before performing the evaluation of ctDNA, primary tumor analysis is required. Hence, 15 representative slides (10µm) must be collected instead. Samples will be shipped to the central laboratory (Erasmus hospital) at fixed time points for evaluation.

The aim is to elucidate the biology of breast cancer in young women. Techniques will comprise but not restricted to immunohistochemistry, in situ hybridization, expression profiling and sequencing. Extraction of nucleic acids (DNA and RNA) may be required to perform these analyses.

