To evaluate the safety of performing a controlled ovarian stimulation with or without letrozole in young women with newly diagnosed breast cancer who are candidates to receive (neo)adjuvant chemotherapy, the following endpoints will be assessed:

- Invasive disease-free survival (iDFS) defined as the time from study inclusion to the first appearance of the following invasive events: local recurrence, distant metastases, contralateral or ipsilateral breast tumor, second primary malignancy, or death from any cause;
- Breast cancer-free interval (BCFI) defined as the time from study inclusion to the first appearance of the following invasive events: local recurrence, distant metastases, contralateral or ipsilateral breast tumor;
- Overall survival (OS) defined as the time from study inclusion to death from any cause;
- Kinetic of circulating tumor DNA (ctDNA) assessed before, after stimulation and during study follow-up (if disease relapse).
- Complications associated with any of the procedure used for oocyte/embryo cryopreservation.

The safety of performing controlled ovarian stimulation with or without letrozole will be evaluated in various subgroups of young women with newly diagnosed breast cancer who are candidates to receive (neo)adjuvant chemotherapy according to the following characteristics:

- Stage at diagnosis: I vs. II vs. III;
- Hormone receptor status: positive vs. negative;
- HER2 status: positive vs. negative;
- Type of exposure to chemotherapy: prior to surgery (neoadjuvant) vs. post surgery (adjuvant);
- Exposure to endocrine therapy: exposure vs. no exposure;
- Presence of *BRCA* mutation: *BRCA*-mutated vs. *BRCA*-not mutated;
- Baseline ctDNA level: present vs. absent.

The following baseline characteristics of young women with newly diagnosed breast cancer who undergo controlled ovarian stimulation with or without letrozole will be assessed:

- Body-Mass Index (BMI) and body surface;
- Smoking history;
- Age at menarche;
- Prior pregnancies (completed, induced or spontaneous abortion);
- Prior treatment for infertility;
- Prior use of birth control pills;
- Prior gynecological diseases with potential impact on reproductive potential;
- Baseline ovarian reserve and function analysis.

Furthermore, the following characteristics of protocols with or without letrozole used for controlled ovarian stimulation in young women with newly diagnosed breast cancer who are candidates to receive (neo)adjuvant chemotherapy will be evaluated:

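### iDFS and BCFI start with the tumour in place in neoadjuvant women but do not count locoregional progression before surgery, so the safety comparison is less able to detect tumour growth

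*Combined protocol and SAP*

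**What the plan says.** - **Time origin.** Section 5 defines both iDFS and BCFI as "time from study inclusion to the first appearance of the following invasive events". Section 4.4 takes the enrolment sample "at the time of oncofertility counseling/breast cancer diagnosis) before starting chemotherapy", and Section 4.3 places enrolment at the same point. In stimulated women this is also before stimulation.
- **Events.** For iDFS the list is "local recurrence, distant metastases, contralateral or ipsilateral breast tumor, second primary malignancy, or death from any cause". BCFI uses the same list without second primary malignancy and death.
- **Population.** Section 5 includes candidates for neoadjuvant as well as adjuvant chemotherapy, and makes the timing of chemotherapy a safety subgroup factor.
- **Contrast.** Section 5 compares each stimulated cohort separately with the non-stimulated cohort for safety.
- **Named worry.** Section 1 reports that many oncologists and patients are uneasy about stimulation, "fearing that the high estrogenic state can promote cancer growth or recurrence".
- **Data.** Section 3.2 item 4 has dated entries for recurrence, contralateral cancer, second malignancy and death, and none for progression. For women given primary systemic therapy, item 2 states that "both clinical tumor size and nodal status before treatment initiation and pathological tumor size and nodal status at the time of surgery will be collected".
- **Short-term marker.** ctDNA kinetics before and after stimulation are a safety endpoint in Section 5. Table 1 schedules plasma at inclusion, at the end of stimulation and at relapse.

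**The concern.** Section 1 mentions two feared effects of high estradiol: growth of the existing cancer, and recurrence. Recurrence has time-to-event endpoints. Growth does not, although in neoadjuvant women the tumour is still there during stimulation and the clock is already running.

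If such a tumour advances in the breast or nodes before surgery, or becomes inoperable, nothing on either event list is triggered at that moment. The woman remains event-free until distant metastasis, a new primary, death (iDFS only) or, if she is operated on, a later local recurrence. If stimulation raised the rate of pre-surgical progression, the planned comparison would miss those events or register them late. As the eCRF asks for no progression date, the date might not be recoverable at analysis.

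**Working it through.** **1. The plan's own figure.** The documents give no event count, hazard ratio, margin or power for iDFS or BCFI. The only sample size is for mature oocytes: 113 per stimulated cohort, difference 1.5, SD 4.0, two-sided alpha 0.05, power 0.80. The normal approximation gives n = 2 × (1.960 + 0.842)² × 4.0² / 1.5² = 111.7, rounded up to 112. The exact t-test calculation gives 113, with power 0.801. The figure reproduces and has no bearing on this point. It supplies only the cohort sizes used in step 5.

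**2. Definition against clinical course.** Consider a neoadjuvant woman from inclusion to surgery.

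| Event before surgery | iDFS | BCFI |
|---|---|---|
| Distant metastasis | counted | counted |
| Contralateral breast tumour | counted | counted |
| Second primary malignancy | counted | not counted |
| Death | counted | not counted |
| Locoregional progression of the index tumour | not listed | not listed |
| Progression that prevents surgery | not listed | not listed |

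Local recurrence presupposes that the tumour has been removed. Ipsilateral breast tumour is not defined for a woman whose index tumour is still in the breast, so one site might code progression there and another might not. The two stimulated cohorts are separated by country (Belgian and French centres), so a national difference in coding would become a cohort difference.

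**3. Does ctDNA fill the gap?** Only partly. The second plasma sample is tied to the end of stimulation. Women in the non-stimulated cohort have no such time point, so the safety comparator has no matching before-and-after change. A marker level is also not a clinical event.

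**4. Do the collected sizes fill the gap?** No. One measurement is clinical and taken before treatment; the other is pathological and taken at surgery. The chemotherapy course lies between them, and no size is planned at the end of stimulation. The pair may show net growth by surgery, but not growth during stimulation that chemotherapy later reversed, and it gives no event date.

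**5. Size.** The documents give neither the neoadjuvant share nor the pre-surgical progression rate. Both are assumed here, at the same values in every cohort. Uncounted events = cohort size × neoadjuvant share × progression rate.

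| Assumed share, rate | Stimulated cohort, n = 113 | Non-stimulated cohort, n = 339 |
|---|---|---|
| 40%, 2% | 113 × 0.40 × 0.02 = 0.9 | 339 × 0.40 × 0.02 = 2.7 |
| 60%, 5% | 113 × 0.60 × 0.05 = 3.4 | 339 × 0.60 × 0.05 = 10.2 |

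With a wider range (share 30-70%, rate 1-5%), the figures are 0.3-4.0 and 1.0-11.9.

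**The case against.** The case on the other side has real force.

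- **The same rule applies to both groups.** The safety contrast is stimulated against non-stimulated, and within neoadjuvant women one event list serves both. A reader might infer that the neoadjuvant subgroup is biased toward looking safe because adjuvant women cannot progress before surgery. The documents do not support this. Neoadjuvant against adjuvant is not a planned safety contrast, and women who later receive adjuvant chemotherapy may also be included before surgery, since inclusion is at counselling or diagnosis. What remains is lost sensitivity.
- **The lists are broader than recurrence.** A reader might say that only recurrence-type events count. In fact iDFS also includes second malignancy and death, and distant metastasis before surgery counts in both endpoints. Progressions that lead to metastasis are eventually picked up by both, and those that lead to death by iDFS and OS. The gap is narrower: locoregional progression, at the time it occurs.
- **Section 1 reports a fear, not an objective.** This is correct. The safety objective names complications, iDFS, BCFI, OS and ctDNA, and all have endpoints. Still, that fear is the protocol's reason for looking at safety.
- **Other routes exist.** Section 7.2 keeps adverse events reportable when they are unexpected or suspected to be linked to stimulation, so a progression need not go unseen. That is not an endpoint and gives no systematic comparison.
- **Few events are expected.** This stands. On the assumed rates most fall in the non-stimulated cohort because it is three times larger, and a stimulated cohort may have one to three. No useful subgroup test can be built on that number alone. It argues for a modest fix, since the definition and the dated field cost little while an uncollected date may be lost.

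**Conclusion.** The point holds as a gap in endpoint definition and data capture. In neoadjuvant women, iDFS and BCFI start while the tumour is in place and do not count its locoregional progression before surgery. The term ipsilateral breast tumour is ambiguous in that period. The stimulated versus non-stimulated comparison in these women is therefore less able to detect growth of the existing cancer, and ctDNA makes up for this only in part.

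The size is small and uncertain: on the assumptions above, a few events per stimulated cohort and up to about ten among controls. These are events missed at the time they occur; some would enter later as listed events. A reader might add the cohorts together and quote about 4-14 missed progressions (0.9 + 2.7 = 3.6 to 3.4 + 10.2 = 13.6). That total is one stimulated cohort plus controls, rests wholly on assumed rates, and says nothing about a difference between cohorts.

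A reader might also conclude that the data needed are already collected and merely unused. They are not, because the paired sizes cannot isolate growth during stimulation or date a progression. The primary endpoint and its sample size are unaffected. The change is worth making, but nothing else in the plan depends on it.

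**What to change.** 1. In Section 5, add event-free survival from inclusion for neoadjuvant women. It would count all iDFS events plus invasive locoregional progression before surgery, or progression that prevents surgery. Use it for the neoadjuvant safety subgroup, with each stimulated cohort compared with the non-stimulated cohort. Leave iDFS and BCFI otherwise as they are.
2. In the same section, state that ipsilateral breast tumour does not cover the unresected index tumour.
3. In Section 3.2 item 4, add progression before surgery, with its date.
4. If pathological response at surgery is compared between cohorts, label it descriptive only, since it mainly reflects chemotherapy.

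The cost is one eCRF field, a few lines of text and one more secondary endpoint with few expected events. It should be reported with estimates and intervals, and not relied on for a test.

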The impact of anticancer therapies on patients' ovarian function will be evaluated in various subgroups of young breast cancer patients according to:

- Age: <30 vs. 30-35 vs. > 35;
- Type of chemotherapy received: anthracycline- and taxane-based vs. taxane-based vs. others;
- Number of months of chemotherapy received: <4 months vs. > 4 months;
- Exposure to platinum agents: use vs. no use.
- Exposure to endocrine therapy: use vs. no use.
- Exposure to anti-HER2 therapy: use vs. no use.
- Presence of *BRCA* mutation: *BRCA*-mutated vs. *BRCA*-not mutated.

The sample size has been estimated based on the study primary endpoint (i.e. number of mature oocytes collected). With 113 patients in the standard-stimulated cohort and 113 in the letrozole-stimulated cohort, assuming a mean number of mature oocytes collected of 6.1 in the standard-stimulated cohort, the study will have a power of 0.80 to reject the null hypothesis of equal means when the population mean difference is 1.5 mature oocytes collected (estimating a mean number of mature oocytes collected of 7.6 in the letrozole-stimulated cohort) with a standard deviation for both groups of 4.0 and with a significance level (alpha) of 0.05 using a two-sided two-sample equal-variance t-test. Considering that approximately one out of three (1:3) eligible patients counseled to

undergo controlled ovarian stimulation for oocyte cryopreservation before starting anticancer treatments will accept the procedure, it is estimated to enroll 339 patients in the non-stimulated cohort.

Patients demographic, clinical and pathologic baseline characteristics will be compared in the three cohorts using chi-square test or Fisher Exact test for categorical variables and Wilcoxon rank-sum test or t-test for continuous variables, as appropriate.

Dicothomous outcomes will be compared using univariate and multivariate logistic regression models. Time-to-event outcomes will be estimated and plotted using Kaplan-Meier methods. Survival rates will be compared using log-rank test and Cox proportional hazards models for univariate and multivariate analysis, respectively.

All tests will be two-sided and p-values of  $< 0.05$  will be considered statistically significant.

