## 7.2. Informed consent form

It is the responsibility of the principal investigators or a person designated by the principal investigators (if acceptable by local regulations) to obtain a signed written informed consent from each potential subject prior any study related procedure being carried out. The informed consent is applicable throughout the subject's participation to the study.

The Informed Consent form (ICF), approved by an appropriate IEC / IRB, is provided by the sponsor to the principal investigators as a separate document dated and version controlled to this protocol.

The ICF describes in details the aims, the procedures, the methods, the interventions, the anticipated benefits, the possible adverse events and the potential hazards of the study. Many events are likely to occur which meet the definition of serious adverse events and which are due explicitly to the patients' underlying malignancy management or chemotherapy treatment. For this study, these adverse events or SAE will be exempt from report or declaration in the CRF, except if unexpected or suspected to be linked to the ovarian stimulation.

The principal investigators or designee also explain to the subject that the participation to the study is voluntary and that the subject is free to refuse to enter the study or to withdraw from it at any time, for any reason without any impact in the subject's subsequent care.

All subjects receive the appropriate version of the written information and are asked to read and review it.

For subjects not qualified to give or incapable of giving consent, written consent must be obtained from the legal representative. In the case where both the subject and his or her legal representative are unable to read, an impartial witness should be present during the entire informed consent discussion. After the subject and/or legal representative has/have orally consented to participation in

the trial, the witness's signature on the form will attest that the information in the consent form was accurately explained and understood.

The written ICF must be dated and personally signed by the principal investigators or authorised sub-investigator and the subject taking consent (or subject legal representative).

The original copy of the signed ICF will be retained in investigator's study file (ISF) and must be made available for monitoring, audit or inspection. A copy of the signed ICF is given to the subject.

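### BCFI counts no death from breast cancer and no cause of death is listed for collection, so a breast cancer death without a dated recurrence is censored as if disease-free

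*Combined protocol and SAP*

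**What the plan says.** Section 5 (STATISTICS) names three time-to-event safety endpoints, all measured from study inclusion.

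- **BCFI.** The definition opens "Breast cancer-free interval (BCFI) defined as the time from study inclusion to the first appearance of the following invasive events". The events are the "following invasive events: local recurrence, distant metastases, contralateral or ipsilateral breast tumor". The list ends there.
- **iDFS.** The bullet directly above BCFI has the same events and adds "second primary malignancy, or death from any cause".
- **OS.** "Overall survival (OS) defined as the time from study inclusion to death from any cause".

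Section 3.2, item 4 (survival status), collects "any recurrence of invasive breast cancer including date of the event", the type of recurrence, contralateral and other second primaries with dates, and "date of last follow-up and/or death". Cause of death is not among the listed items.

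For the analysis, Section 5 says "Time-to-event outcomes will be estimated and plotted using Kaplan-Meier methods" and names the log-rank test for univariate and Cox models for multivariate comparisons. It states no censoring rule and no method for competing events. Each stimulated cohort is compared separately with the non-stimulated cohort.

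**The concern.** BCFI is the only time-to-event safety endpoint in the plan that is specific to breast cancer. iDFS also counts second malignancies and deaths from any cause, and OS counts all deaths. A death from breast cancer is direct evidence that the disease came back or progressed, whether or not anyone dated the recurrence. Under the definition as written, that evidence is not used unless a recurrence was recorded first.

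The woman instead leaves the risk set as censored. Kaplan-Meier, log-rank and Cox then treat her as having the same future risk as women still under observation, when she has in fact already failed. Within any cohort where this happens, the BCFI curve is too favourable. The hazard ratio is also distorted if it happens at different rates in the two cohorts compared.

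The problem cannot be fully repaired at the analysis stage, because the listed data do not separate breast cancer deaths from other deaths.

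**Working it through.** **1. The plan's own figures.** No event count, event rate or power is stated for BCFI, so there is nothing to reproduce for this endpoint. The only sample size is for mature oocytes: difference 1.5, SD 4.0, two-sided alpha 0.05, power 0.80. The exact two-sample t-test gives 112.6 per group, rounded up to 113, with power 0.801 at 113. That reproduces the plan and is unaffected by this point.

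**2. The definitions side by side.** The table applies the Section 5 definitions to the data listed in Section 3.2.

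| Course | BCFI | iDFS | OS |
|---|---|---|---|
| Recurrence dated, then death from breast cancer | event at recurrence | event at recurrence | event at death |
| Death from breast cancer, no dated recurrence | censored | event at death | event at death |
| Death from another cause, no earlier event | censored | event at death | event at death |
| Death of unknown cause, no earlier event | censored | event at death | event at death |

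The first row is handled correctly. The second is the defect. With only a death date listed, the last three rows look alike in the data, apart from what a recorded second primary or a reported SAE may reveal. The SAE route is incomplete: for events due to management of the malignancy or to chemotherapy, Section 7.2 says "these adverse events or SAE will be exempt from report or declaration in the CRF", unless they are unexpected or suspected to be linked to stimulation.

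The word censored is an inference, since no censoring rule is written. It follows from the text: a death that is not an event and has no earlier event date can only end follow-up.

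**3. Events lost (assumed rates).** One stimulated cohort against the non-stimulated cohort is 113 + 339 = 452 women. Assume that 10-20% have a BCFI event, and that 2-10% of those are breast cancer deaths with no dated recurrence. Neither figure is in the documents.

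- At 10%: 452 × 0.10 = 45.2 events. Lost: 45.2 × 0.02 = 0.9 to 45.2 × 0.10 = 4.5.
- At 20%: 452 × 0.20 = 90.4 events. Lost: 90.4 × 0.02 = 1.8 to 90.4 × 0.10 = 9.0.

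**4. Power.** Schoenfeld's formula is power = Φ(√(d × 0.25 × 0.75) × ln HR − 1.96), where d is the number of events and 113/452 = 0.25. For an assumed HR of 2:

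| Event rate | No loss | 2% lost | 10% lost |
|---|---|---|---|
| 10% | 0.52 | 0.52 | 0.48 |
| 15% | 0.70 | 0.69 | 0.65 |
| 20% | 0.81 | 0.81 | 0.77 |

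The largest fall is about 0.05.

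**5. Hazard ratio.** If a fraction f_s of events is lost in the stimulated cohort and f_n in the non-stimulated cohort, the apparent HR is roughly the true HR × (1 − f_s)/(1 − f_n). With a true HR of 1.0:

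- 5% lost in both cohorts: 0.95/0.95 = 1.00.
- 5% lost in the stimulated cohort only: 0.95.
- 5% lost in the non-stimulated cohort only: 1/0.95 = 1.05.

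The documents do not say which pattern applies.

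**The case against.** The strongest reply is that the definitions are coherent as a set. BCFI measures recurrence, iDFS adds death, and OS is death. Most breast cancer deaths should follow a recorded recurrence and so are already BCFI events. A missing recurrence date may also be recoverable from hospital records, which Section 8.1 names as source documents. No death drops out of the safety evaluation as a whole. A Cox model that censors other-cause deaths is already a cause-specific Cox model, so no new model is needed. The eCRF itself is not part of the documents, so the most that can be said is that cause of death is not listed.

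All of this stands, and it limits the size of the problem. It does not answer the remaining case: where no recurrence date is found, no rule lets the analyst use the death as evidence of breast cancer, and nothing listed identifies which deaths those are.

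A reader might go further and infer that the loss falls mainly on the non-stimulated cohort and so makes stimulation look worse than it is. Two features suggest this: the gap in Table 1 between months 28-30 and month 60, and the idea that these women have no stored material to bring them back. The documents do not support it. Table 1 schedules samples for correlative research and is not an oncologic follow-up calendar. Its post-chemotherapy serum row is not restricted to stimulated women, and it has a relapse column. Section 5 admits women with cryopreserved ovarian tissue to the non-stimulated cohort. Section 3.2 records recurrence as survival status, without tying it to fertility clinic visits.

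**Conclusion.** The point holds in a limited form. BCFI as defined censors a breast cancer death that has no dated recurrence, and the listed data do not identify such deaths. This follows from the stated definition, the stated data items and the stated methods. The only inference is the censoring step.

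The size is not given and is probably small: about 1 to 9 events per comparison and at most about 0.05 of power, under the assumed event rates, lost shares and HR of 2. Within a cohort, the BCFI curve errs on the favourable side. For the hazard ratio the direction is unknown, and equal proportional loss leaves it near its true value. No claim of bias for or against stimulation is supported. iDFS, OS and the primary-endpoint sample size are unaffected. It is a cheap improvement to a secondary endpoint.

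**What to change.** 1. **Section 3.2, item 4:** add cause of death, coded as breast cancer, other or unknown.
2. **Section 5, BCFI definition:** count death from breast cancer without prior recurrence as a BCFI event at the date of death.
3. **Section 5, analysis:** state that deaths from other causes are censored in the Cox model, which is then explicitly cause-specific. Cumulative incidence can be shown as an optional display.
4. **Sensitivity analysis:** repeat the BCFI comparison with unknown-cause deaths without recurrence counted as events.

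The cost is one eCRF field and a few sentences in the plan. The drawback is some misclassification of cause of death, which the sensitivity analysis addresses in part. The field is best added while data are being collected: Section 7.3 says the sponsor does not record names, so later recovery would have to go back through the sites.
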